7.3 Interim Analysis

No interim analysis is planned in this study.

7.4 Missing Data

Missing data will not be imputed except of the missing AE data which are specified in section 9.1.

8. DEMOGRAPHICS, BASELINE CHARACTERISTICS AND STUDY SUMMARY

All demographic and baseline characteristics summaries are to be performed on the entered and evaluable analysis sets, unless stated otherwise.

8.1 Subject Disposition

The number and percentage of subjects who were screened, signed informed consent, completed, and discontinued, including discontinuation period, will be summarized. The number and percentage of subjects who discontinued will also be summarized for each reason for discontinuation. The summary will be made overall and by study site.

8.2 Demographics and Baseline Characteristics

The demographics (age, gender, ethnicity, and race) and baseline body weight and height, as well as the number of subjects in each of the categorized baseline variables, including HbA1c ($\leq 9.0\%$ vs. $> 9.0\%$), and duration of diabetes (\leq median vs. $>$ median), will be summarized using descriptive statistics. Additionally, the age will be grouped into the following categories and summarized: less than 65 yrs, 65 to 84 yrs, and greater than 84 yrs.

The duration of diabetes will be calculated in months using the following formula rounding to one decimal place.

CCI

8.3 Medical History

The medical history will be coded by MedDRA 20.1. The summary will be made by MedDRA SOC and Preferred Terms.

8.4 Diabetes Diagnosis

The Type of diabetes, duration of diabetes, and pre-enrollment bolus insulin analog collected at screening will be summarized by descriptive statistics.

8.5 Big Five Inventory (BFI)

The BFI is a 44-item inventory that measures an individual on the Big Five Factors (dimensions) of personality, Extraversion versus introversion (8 items), Agreeableness versus antagonism (9 items), Conscientiousness versus lack of direction (9 items), Neuroticism versus emotional stability (8 items), and Openness versus closedness to experience (10 items). The evaluation uses a Likert scale of (1) disagree strongly, (2) disagree a little, (3) neither agree nor disagree, (4) agree a little, and (5) agree strongly.

The results on the Likert scale in the five categories will be summarized by descriptive statistics using frequency and percentage.

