9.1.3. Exploratory Assessments

Study IOQV will possibly explore 6 different PRO evaluations that the subject will perform at time points outlined in the SOA ([Table IOQV.1](#)). These PRO evaluations are the Hypoglycemic Confidence Scale (HCS), Adult Low Blood Sugar Survey (ALBSS), the Big Five Inventory (BFI), Health Problem Solving Scale (HPSS), the Pictorial Representation of Illness and Self Measure Revised II (PRISM R II), and the General Life Stress Scale (GLSS). The details of each PRO evaluation are listed in the following sections.

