9.1.3.3. The Big Five Inventory

The BFI is 44-item inventory that measures an individual on the Big Five Factors (dimensions) of personality, Extraversion versus introversion (8 items), Agreeableness versus antagonism (9 items), Conscientiousness versus lack of direction (9 items), Neuroticism versus emotional stability (8 items), and Openness versus closedness to experience (10 items). Identifying a patient's thinking, feeling, and behaving may help clinicians avoid suggesting solutions that will not work for that patient's personality type (APA WWW). The evaluation uses a Likert scale of (1) disagree strongly, (2) disagree a little, (3) neither agree nor disagree, (4) agree a little, and (5) agree strongly. (Goldberg 1981).

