10.3.4. Other Analyses

Patient reported outcomes rated on the Likert scale will be summarized using frequency and percentage. Domain or total scores will be summarized using: n, mean, SD, minimum, median, maximum at the times outlined in the SOA ([Table IOQV.1](#)).

In addition, bolus dose, basal insulin dose information, and exposure will be summarized.

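### SAP 8.5 summarises the Big Five Inventory only as response frequencies and prespecifies none of its five dimension scores, so the exploratory analysis has no personality variable to use

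*SAP*

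**What the plan says.** Protocol 9.1.3 names the BFI as one of the PRO evaluations ("Study IOQV will possibly explore 6 different PRO evaluations that the subject will perform at time points outlined in the SOA"). Protocol 9.1.3.3 says that it "measures an individual on the Big Five Factors (dimensions) of personality" and lists five dimensions with 8, 9, 9, 8 and 10 items. SAP 8.5 repeats this description ("The BFI is a 44-item inventory that measures an individual on the Big Five Factors (dimensions) of personality") and the five response options.

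Protocol 10.3.4 sets out two levels of PRO summary:

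- For responses: "Patient reported outcomes rated on the Likert scale will be summarized using frequency and percentage".
- For scores: "Domain or total scores will be summarized using: n, mean, SD, minimum, median, maximum at the times outlined in the SOA".

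For the BFI, SAP 8.5 carries out the first level only: "The results on the Likert scale in the five categories will be summarized by descriptive statistics using frequency and percentage". It gives no dimension score, no list of which items belong to which dimension, and no statement on item direction. Nothing in that section appears to be blacked out.

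Elsewhere in the SAP the BFI appears in the schedule (once, at Visit 1), in Tables 14.1.5.1 and 14.1.5.2, and in Listing 16.2.4.4. The figures in SAP 11.2 cover the other five PROs and not the BFI.

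**The concern.** An instrument described as measuring a person on five dimensions is normally reported as five values per person. A table of how many subjects chose each response to each statement describes the statements. It does not say how conscientious or how neurotic any subject is, and it cannot be set against that subject's glucose data.

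This bears on the exploratory objective of evaluating characteristics associated with short-term glycemic control, whose endpoint is the outcome of each PRO instrument. Protocol 9.1.4 says the PROs are there to help understand behavior and its relationship with bolus dosing. If SAP 8.5 is followed exactly, every subject answers 44 items and the planned tables hold no subject-level personality value to describe or relate to time-in-range or missed doses.

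**Working it through.** **Item count.** The dimension sizes in SAP 8.5 add to 8 + 9 + 9 + 8 + 10 = 44, which agrees with the stated total. The description of the instrument is therefore complete down to the size of each dimension; what is absent is the step from items to scores.

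**Meaning of the five categories.** The SAP writes of four categories for the four-option Hypoglycemic Confidence Scale (HCS, 10.5) and of five categories for the five-option Adult Low Blood Sugar Survey (ALBSS, 10.6) and Health Problem Solving Scale (HPSS, 10.7). The General Life Stress Scale (GLSS, 10.9) has six areas of life summarised in five categories. The word therefore most likely means response options. If it meant the five dimensions in 8.5, the output would still be frequencies and percentages.

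**Comparison within the SAP.**

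| Instrument | Frequencies of responses | Score defined | Score summarised | Plot against time-in-range |
|---|---|---|---|---|
| HCS (10.5) | yes | yes | yes | yes |
| ALBSS (10.6) | yes | yes, two domains and total | yes | yes |
| HPSS (10.7) | yes | yes, seven subscales and total | yes | yes |
| GLSS (10.9) | yes | yes | yes | yes |
| BFI (8.5) | yes | no | no | no |

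The remaining PRO, the PRISM (10.8), is not a Likert instrument, but its two measures are summarised and its separation measure is plotted. For the HPSS the SAP prints a key in which each of items 1 to 50 appears exactly once, and it reverses the negative subscales. The BFI has no counterpart.

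**What the planned output can hold.** With one row per item, the BFI table has at most 44 × 5 = 220 item-by-response cells and 0 of 5 dimension scores.

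**Can scores be recovered from those cells?** Take assumed data, not trial data: 50 subjects and one 8-item dimension, with every item answered by 10 subjects (20%) in each of the five options. The score is the mean of the 8 items. In all three cases below the item-frequency table is identical and the mean score is 3.0.

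| How the answers go together within subjects | SD | Minimum | Maximum |
|---|---|---|---|
| Each subject gives the same answer to all 8 items | 1.43 | 1.0 | 5.0 |
| Items unrelated (one random shuffle) | 0.48 | 1.875 | 4.0 |
| Four items run opposite to the other four and are not reversed | 0.00 | 3.0 | 3.0 |

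The first SD is √[10 × (4 + 1 + 0 + 1 + 4)/49] = √(100/49) = 1.43. For unrelated items the expected SD is about 1.43/√8 = 0.51, and the shuffle gave 0.48. In the third case each subject's mean is (4x + 4(6 − x))/8 = 3 whatever the answer x. Reversing the four opposed items turns the third case into the first.

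The frequency table therefore does not fix the SD, minimum or maximum of the score; nor, in general, does it fix the median, although this symmetric example does not show that. Only a group mean could be rebuilt, and only from per-item tables combined with a scoring key that the SAP does not give.

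**The case against.** The strongest objection is that SAP 8.5 does what the protocol says for Likert responses, and that the sentence on domain or total scores neither names the BFI nor requires every instrument to have a score. Protocol 9.1.3.1, 9.1.3.2 and 9.1.3.4 to 9.1.3.6 specify a score or extracted measure for each of the other five PROs; 9.1.3.3 specifies none for the BFI. This stands. A reader might infer that the SAP contradicts an explicit protocol requirement, but the documents support only that a general rule, applied to an instrument described by five dimensions, has been half carried out.

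A reader might also infer that the BFI information is lost, or that personality can no longer be studied. The documents do not support that either. Responses are tabulated and listed, and Protocol 10.3.1 allows additional exploratory analyses, so scores could be formed later. What is missing is the prespecified output.

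Neither document says that any BFI item is reverse-keyed or how a dimension is scored. The third row of the illustration is therefore conditional, and the point does not depend on it: the first two rows need no reversed items.

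Finally, importance is limited. The PRO endpoint is footnoted as depending on availability, the BFI is a single baseline measure, and the study is descriptive. This bears on priority, but it does not supply the missing scores. The absence of a BFI table shell proves nothing either way, since SAP 12 shows only a few shells and says that they are not exhaustive.

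**Conclusion.** The point holds as a gap in prespecification. SAP 8.5 stops at response frequencies for an instrument that both documents describe by five dimensions, while the four other Likert instruments receive a defined score, a summary and a plot, and no reason for the difference is given. Followed exactly, the plan yields none of the five trait scores for any subject and does not relate personality to glycemic control.

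The size is modest. One exploratory objective is affected; the primary and secondary endpoints, safety and sample size are not. The conclusion rests on the SAP text and on reading the general score rule in Protocol 10.3.4 as covering the BFI as one of the listed PROs. The SDs rest on assumed data and show only that frequencies do not determine scores; they do not predict what this trial would find. It should be corrected, but it does not threaten the study's main results.

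**What to change.** In SAP 8.5:

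1. Form five dimension scores per subject from the instrument's published scoring key. Print in the SAP which items belong to each dimension and which, if any, are reversed, as SAP 10.7 does for the HPSS.
2. State a rule for partly answered dimensions that agrees with SAP 7.4, which allows no imputation outside adverse events. The simplest is to leave a dimension score missing unless all its items are answered. Averaging only the answered items amounts to filling the gaps with the subject's own mean, so it would have to be declared as an exception.
3. Summarise the five scores in Tables 14.1.5.1 and 14.1.5.2 in the form that Protocol 10.3.4 gives ("Domain or total scores will be summarized using: n, mean, SD, minimum, median, maximum"), and add them to Listing 16.2.4.4. Keep the response frequencies as a supplement.
4. Add to SAP 11.2 scatterplots of each baseline score against percent time-in-range in each period: 5 scores × 2 periods = 10 panels. The BFI is given once, so the baseline score takes the place of the change from baseline used for the other PROs. Without this step the scores would be described but still not related to glycemic control.

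The cost is SAP wording, a short scoring program and these few outputs. No new data are needed.

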8.6 Treatment Compliance

The total number of measures from the CGM device and pen per subject during the analysis periods (refer to the definition 3 in section 10.1) will be summarized for the evaluable analysis set. Note that among the several records captured for each injection in the Pen data, observations not more than 30 minutes apart will be considered one injection (refer to the definition 2 in section 10.1).

9. ANALYSIS OF SAFETY ENDPOINTS

All safety summaries are to be performed on the safety analysis set by period, unless stated otherwise.

9.1 Adverse Events

The adverse events will be coded by the Medical Dictionary for Drug Regulatory Activities (MedDRA) version 20.1.

All adverse events (AE) occurred post screening will be presented in the summary tables.

Summary tables will include the number and percentage of subjects reporting adverse events. The number of serious adverse events may be summarized in the appropriate summary table(s). Summary tables will also be presented for the frequency of adverse events by the MedDRA system organ class and preferred term. Multiple events in the same system organ class for a subject are only counted once in the statistics of that system organ

class. Summary tables will also be presented for the frequency of adverse events by MedDRA system organ class and preferred term and severity of adverse events, and relationship of adverse events to insulin, pen, or CGM respectively. In these summaries, the most extreme outcome (highest severity) will be used for those subjects who experience the same adverse event (per preferred term) on more than one occasion. A listing of adverse events that lead to discontinuation from the study will also be provided.

Missing values will be treated as missing except for causality and severity of an AE, at which occurrence a “worst case” approach will be taken in the analysis. Thus, if causality is missing the AE will be regarded as related to insulin, pen, and CGM, and if the severity is missing the severity of the AE will be regarded as severe. If the seriousness is missing, all efforts should be made prior to database lock to make sure that this information is available.

9.2 Concomitant Medications

The concomitant medications will be coded by WHO ATC classification, and summarized by descriptive statistics for the safety analysis set disregard of the periods.

9.3 Bolus Insulin Regimen and Dose Change

The data collected in the CRF Bolus Insulin Regimen at screening and CRF Bolus Insulin Dose Change at post screening visits will be summarized. The focus will be on the dose change (Yes or No). The detail of the bolus insulin regimen will be presented in the data listing(s).

[figure not shown]
10. ANALYSIS OF EFFICACY ENDPOINTS

[figure not shown]
All efficacy summaries are to be performed on the evaluable analysis set by period. The GCM and Pen data collected for Weeks 3-6 (Visits 2 and 3) for Study Period 1 (blinded CGM) and Weeks 9-12 (Visits 4 and 5) for Study Period 2 (unblinded CGM) will be used in these calculations. The inclusion of the data will be based on the dates, disregard of the times even available, of the visits, which means that the GCM and Pen data will be included for the Study Period 1 if they are in the range from the date of the Visit 2 to the date of the Visit 3, inclusive, and included for the Study Period 2 if they are in the range

from the date of the Visit 4 to the date of Visit 5, inclusive. If a subject discontinues the study, the date of Early Termination will be used instead.

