Visit Window	N/A	3D	3D	3D	3D	N/A	Allowable deviation +/- days or weeks from scheduled visit.
Office or home visit	X	X	X	X	X	X	
Informed consent	X						
Inclusion and exclusion criteria	X						
Demography	X						
Height and weight	X						
Medical history	X						
Current medical conditions	X						Including baseline diabetes disease characteristics
Pregnancy test	X						
Prescribed insulin regimen	X						Currently prescribed basal and bolus insulin regimen
Concomitant medication review	X	X	X	X	X	X	
Enrollment	X						
HbA1c blood draw ^a	X		X		X	X	
Pen dispensing	X						Record pen identification for dispensed pens
Pen training and start pen	X						
Confirm pen operation		X	X	X	X		
Pen collection/return					X	X	
CGM and glucose meter training	X						
CGM and pen data download		X	X	X	X	X	
Adjust CGM alert settings				X			
Hypoglycemic Confidence Scale	X		X		X	X	
Adult Low Blood Sugar Survey	X		X		X	X	

	Study Period 1 Blinded CGM			Study Period 2 Unblinded CGM			
The Big Five Inventory	X						
Health Problem Solving Scale	X		X		X	X	
Pictorial Representation of Illness and Self Measure	X		X		X	X	
General Life Stress Scale	X		X		X	X	
AE and SAE review		X	X	X	X	X	
Product complaint review		X	X	X	X	X	

Abbreviations: AE = adverse event; CGM = continuous glucose monitoring; D = days; D/C = discontinuation; HbA1c = glycated hemoglobin; N/A = not applicable; SAE = serious adverse event; V = visit; W = week.

^a HbA1c testing will be performed by local laboratories.

3. Introduction

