Subjects will be instructed to insert a new sensor weekly and recalibrate the CGM device throughout the study. At Visit 2 (Week 3) and Visit 3 (Week 6), subjects will have their blinded CGM data and pen data downloaded by the study site personnel.

5.1.3. Study Period 2

Following the completion of Visit 3 (Week 6) assessments, subjects will begin Study Period 2 and will be unblinded to their CGM data.

At Visit 4 (Week 9), subjects will have their unblinded CGM data and pen data downloaded by the study site personnel and any required adjustments to their CGM device alarms will be performed by the study site. Insulin adjustment recommendations will be provided by the investigator and designated staff based on the available glucose and insulin data. At Visit 5 (Week 12), subjects will complete their participation in the study, and the site will download all of the pen and CGM data since the last visit.

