7.1. Treatments Administered

This study involves the treatment of subjects with diabetes with marketed insulin lispro (100 units/mL) administered by the pen. Table IOQV.3 shows the treatment regimens. Subjects will continue their pre-study concomitant anti-hyperglycemic medication and basal insulin therapies during the study.

Table IOQV.3. Treatment Regimens

Study Period 1	Study Period 2
Insulin lispro doses as prescribed delivered via the pen. CGM data blinded.	Insulin lispro doses as prescribed delivered via the pen. CGM data unblinded.

Abbreviation: CGM = continuous glucose monitoring.

The investigator or his/her designee is responsible for the following:

- explaining the correct use of the pen, the commercially available CGM device, and the glucometer to the subject or the subject's legal representative.
- maintaining accurate records of all pens, medication vouchers/pharmacy cards, and device dispensing and collection.
- at the end of the study, all pens, the CGM device, and glucose meter must be returned to Lilly or its designee.

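### The last Period 2 date is cut short at the closing visit, so Period 2 missed-dose rates may read slightly low against Period 1 unless the redacted SAP 10.1 allows for it

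*SAP*

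**What the plan says.** SAP 10 gives one rule for both periods: "The inclusion of the data will be based on the dates, disregard of the times even available, of the visits". Period 1 data enter "if they are in the range from the date of the Visit 2 to the date of the Visit 3, inclusive". Period 2 data enter "from the date of the Visit 4 to the date of Visit 5, inclusive". For dropouts, "If a subject discontinues the study, the date of Early Termination will be used instead".

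The device logistics are in the protocol. The row "Pen collection/return" in Table IOQV.1 is marked only at Visit 5 and at early discontinuation. Protocol 7.1 adds that "at the end of the study, all pens, the CGM device, and glucose meter must be returned to Lilly or its designee". Protocol 5.1.3 places the final download at Visit 5, where "the site will download all of the pen and CGM data since the last visit", and Table IOQV.1 also marks a download at early discontinuation. No later download is planned.

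The day count used as a divisor is not readable. Protocol 10.3.2.1 says that three weeks of data are scaled to a month. SAP 8.6 refers to a definition of the analysis periods in SAP 10.1, and that text is redacted.

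**The concern.** The two windows have the same length on paper but close differently. At Visit 3 the subject leaves with the pen and CGM, and the rest of that date is captured at the next download. At Visit 5 or early termination, recording that can reach the database stops at the visit, yet the inclusion rule takes in the whole date.

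Under Protocol 9.1.1 a missed dose needs a CGM excursion with no pen record in the hour before it. A meal after the closing visit therefore cannot yield a detected miss, and a meal shortly before it may lack its two-hour follow-up. If that date still adds a full day to the divisor, Period 2 rates fall with no change in behaviour.

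SAP 6 and Table 14.2.1 set the two periods side by side, and Protocol 3.1 says that differences by CGM blinding will be explored. The artefact would point in the direction that a reader would credit to unblinding.

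**Working it through.** **Plan's own figures.** The documents give no expected missed-dose rate, standard deviation or precision, so there is no planned figure on this point to reproduce. The one derivable planning number, 68/0.85 = 80 screened, reproduces but has no bearing here.

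**Inputs from the documents**
- Scheduled visits are 21 days apart, which gives 22 dates with both ends included.
- Visit windows are ±3 days each, so 15 to 27 days separate consecutive visits: 16 to 28 inclusive dates.
- The only missed-day rate is 3.3 days per month (Protocol 3.1, among patients who reported omission). It is used for illustration.

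**Assumptions, not in the documents**
- Three independent boluses a day, a 30-day month and the same behaviour in both periods.
- k of the three boluses (0, 1 or 2) are observed on the closing date.
- The divisor is the number of dates D.

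**Formulas.** Chance of a day with a miss: q = 3.3/30 = 0.11. Chance per bolus: p = 1 − 0.89^(1/3) = 0.0381. On the closing date: q_k = 1 − (1 − p)^k, which is 0, 0.0381 or 0.0748. Then

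Period 2 days per month = 30 × [(D − 1) × q + q_k] / D.

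For D = 22 and k = 0: 30 × (21 × 0.11)/22 = 3.15, against 3.30 in Period 1.

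| D | k = 0 | k = 1 | k = 2 |
|---|---|---|---|
| 16 | 3.09 (6.2% low) | 3.17 (4.1%) | 3.23 (2.0%) |
| 22 | 3.15 (4.5%) | 3.20 (3.0%) | 3.25 (1.5%) |
| 28 | 3.18 (3.6%) | 3.22 (2.3%) | 3.26 (1.1%) |

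**Count-based rates.** For missed doses per day the relative loss is (1 − k/3)/D. At D = 22 that is 4.5%, 3.0% or 1.5%.

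**Sensitivity to the miss rate.** Assume a detected-miss chance of 0.1 per meal and a 30.44-day month. Period 1 is then 30.44 × (1 − 0.9³) = 8.25 days per month. Period 2 at D = 22 is 7.87, 8.01 or 8.14, which is 4.5%, 2.9% or 1.4% lower. The relative size hardly moves.

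**Fixed 21-day divisor.** Period 1 scales by 22/21 = 1.048. If nothing is seen on the closing date, Period 2 scales by 21/21 = 1.000. The ratio is 21/22, so the maximum gap is again 4.5%.

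**Early termination d days after Visit 4.** The window has d + 1 dates, so the maximum loss is 1/(d + 1): 50% at 1 day, 25% at 3, 12.5% at 7 and 6.7% at 14. Such subjects can still be evaluable, because SAP 5.2 asks for two weeks of unblinded CGM and unblinding begins at Visit 3.

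**Observed-time divisor.** The closing date then contributes only its observed hours, and there is no built-in shortfall.

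**The case against.** The strongest reply is that SAP 10 is a rule for including data and sets no divisor. The derivation is in SAP 10.1, which is redacted and so cannot be called missing. If it divides by usable days or observed time, or drops partial days, the effect shrinks or vanishes. This stands, and it makes the point conditional. A reader might infer that the plan counts the Visit 5 date as a full day, so that Period 2 falls by construction. The readable text does not say so.

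Two further inferences go too far:
- That every Period 1 date is fully observed. Protocol 8.1.2 allows up to 3 days without the pen, sensors are replaced weekly, and the Visit 3 date is only partly blinded. The documents show that the Visit 3 date can be recorded in full, not that it always is.
- That the error has the same sign in every subject. It is zero for a subject with no detectable miss after the visit. For the days endpoint it is also zero where a miss was already detected earlier that date. The shift is on average only.

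The size is also modest. At 3.3 days per month it is 0.05 to 0.15 day, in tables that SAP 11.1 rounds to one decimal. The analyses are descriptive, and the Table 14.2.1 shell has no between-period difference or test. This stands and limits the importance of the point.

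It could be argued that a sensor still worn after the pen is handed in would push the count the other way. That does not hold: with no download planned after the closing visit, such readings would not enter the data.

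**Conclusion.** The point holds in conditional form and is minor. The closing date of Period 2 is cut at the visit, while the closing date of Period 1 need not be. Under a count-of-dates or fixed 21-day divisor, the secondary Period 2 rates per day or month are understated on average relative to Period 1. For completers this is about 1.5% to 4.5% on schedule and at most about 6% with 16 dates. It is much larger only for subjects who terminate soon after Visit 4.

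These figures rest on equal behaviour in both periods, three boluses a day and an assumed number of boluses observed on the closing date. The upper values require that none is observed.

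The primary endpoint uses Period 1 alone and is untouched by this cut. Percent time-in-range needs no day count. Percent of missed doses is affected only if its denominator is prescribed rather than observed doses, which is not readable.

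**What to change.** In SAP 10, end each efficacy window on the day before its closing visit:
- Period 1: Visit 2 date to Visit 3 date minus 1.
- Period 2: Visit 4 date to Visit 5 (or early termination) date minus 1.

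Use the number of those dates as the denominator for the daily and monthly rates, unless SAP 10.1 already uses observed time.

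On schedule both windows are then 21 dates, none of them cut by device return. The change also removes the partly unblinded Visit 3 date from the primary window, and it does no harm if SAP 10.1 already handles partial dates.

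The cost is one line of SAP wording and one date per subject and period (1/22, about 4.5% of the data), including one date from the primary window.
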